Guanfacine is the oldest alpha-2 adrenergic agonist in clinical use in this class.²⁴ Of the alpha-2 agonists, guanfacine has the lowest rate of sedation. 25 Guanfacine is currently approved in tablet form for the treatment of hypertension (1 to 2 mg) and Attention Deficit Hyperactivity Disorder (1 to 4 mg). Guanfacine is readily absorbed with around 80% oral bioavailability and has an elimination half-life of ~17 h with renal excretion accounting for ~50%. Guanfacine has been shown to have similar in vitro potency as clonidine to inhibit conduction in rat sciatic nerve fibers.²⁷ Intrathecal guanfacine has a similar antinociceptive effect as that of intrathecal clonidine in a goat model.²⁸ Guanfacine showed longer antinociceptive effect in comparison to clonidine (8 h vs. 5 h) due to slower elimination of guanfacine from spinal cord tissue. In a rat model, intrathecal guanfacine has shown antinociceptive effect for greater than 18 h (both 25 mcg and 50 mcg) in comparison to clonidine injection (50 mcg) which declined to baseline within 4 h.²⁹ This study also reported a lower rate of elimination of guanfacine from spinal cord tissue compared to clonidine. Highly concentrated guanfacine (75 mcg in 15 µl saline) solution administered through an intrathecal route has been shown to be nontoxic in the subarachnoid space, establishing the safe use of guanfacine for perineural blockade.³⁰ Guanfacine as studied in animals and used in humans has a safe risk profile, suggesting that repurposing it for other indications. Guanfacine has the potential to be developed as a safe, non-opioid, analgesic for acute and chronic debilitating pain. Guanfacine in combination with 1% lidocaine is expected to be safe and to provide an extended duration of pain relief in painful trigeminal neuropathy patients who are not able to obtain pain relief from standard neuropathic pain medication.

PheWAS data indicating the role of the alpha-2-adrenergic receptor in trigeminal nerve pain

BioVU is a large repository of de-identified DNA samples that Vanderbilt University Medical Center (VUMC) has cataloged for >10 years from what otherwise would have been excess, discarded patient blood samples collected during routine clinical testing. Biospecimens within BioVU are linked to corresponding longitudinal clinical and demographic data derived from the Synthetic Derivative, our de-identified database of EMRs. 31-33

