2.0 STUDY DESIGN

Primary Hypothesis:

Due to its different but relevant mechanism of action, guanfacine will be an effective adjunct to lidocaine in trigeminal nerve block for the treatment of painful trigeminal neuropathy by enhancing and prolonging pain relief compared to lidocaine alone.

Endpoints

The following endpoints will be measured to evaluate the exploratory objectives of the study assessing guanfacine and lidocaine in combination compared to lidocaine alone, in pain management in the painful trigeminal neuropathy patient.

- Primary endpoint: time to return to baseline pain (VAS) measurement after treatment with guanfacine as adjuvant to 1% lidocaine compared to 1% lidocaine alone
- Safety endpoint: comparable side effect profile of combination product compared to lidocaine alone on relevant adverse event measures: sedation, local site reaction, confusion
- Secondary endpoint: pain intensity after treatment to be measured throughout the follow-up periods on a visual analog scale (VAS)
- Secondary endpoint: quality of life after treatment to be measured using PROMIS Global Health -10 SF during the follow-up periods
- Secondary endpoint: frequency of acute trigeminal nerve pain attacks during the follow-up periods
- Secondary endpoint: total amount of rescue medications (opioid and non-opioid analgesics) for pain management during the follow-up periods
- Secondary endpoint: time to first rescue medication during the follow-up periods

Experimental Design

The trial is designed as a single-center, randomized, double-blind, controlle, 2x2 crossover pilot study with two arms: study drug (guanfacine and lidocaine combination) and active control (lidocaine alone). The target sample size is 30 study drug vs. 30 active control.

Not all participants that are randomized and initiate the first arm of the trial will *necessarily* complete *both* arms of the crossover trial. Based on previous experience, initiating the first arm of the cross over trial in 40 participants should be sufficient reach the full sample size (30 study drug vs. 30 active control). The trial will be complete and enrollment will cease upon reaching the full proposed sample size (30 study drug vs. 30 active control).

Approximately 80 patients meeting preliminary enrollment criteria will be consented for screening with the goal of roughly half being eligible to randomize and begin participation in the trial.

Inclusion Criteria

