Participants will be asked to record their pain intensity, 24- hour VAS and current VAS, before the procedure to establish a baseline pain score. Other data will be collected for secondary measures: frequency of pain attacks, basal and breakthrough opioid and non-opioid analgesic frequency and dose. Overall quality of life (PROMIS Global-10 short form) will be assessed.³⁹ Women of childbearing potential will undergo a urine pregnancy test prior to receiving the nerve block.

First trigeminal nerve block procedure: Participant will receive either study drug (guanfacine and lidocaine combination) or active control (lidocaine alone) for the trigeminal nerve block based on randomization. Participants will be monitored for pain intensity at 30-minute time intervals for the first 8 hours after block in addition to safety monitoring procedures. Participant responses will be collected at 30 minute intervals for the first 8 hours while in the recovery (first 60 minutes) and after discharge home, with responses allowed all the way until the next time point and actual time of the response being used in analysis. Assessments will be recorded according to the patient's preference, either on paper or via text message) using the Twilio application linked to REDCap. Patients will also receive a sheet with contact information for the study nurse.

First follow-up period (Day 2 to Day 14)

Participants will be monitored once daily at approximately the same timepoint for 14 days using text message generated using the Twilio application or recorded on a paper diary. Participants will also be monitored for any use of rescue medication (analgesics) once daily. The study nurse will monitor participants once weekly for overall quality of life via phone call using the PROMIS global 10 SF. Participants will be instructed to contact the study nurse with any adverse events directly by phone.

At the end of the first follow-up period, participants will be contacted for crossover to the other arm to receive the second trigeminal nerve block using the alternative drug (study drug or active control), not received during the first nerve block. At the second study visit, participants will record 24-hour VAS and current VAS, and the PROMIS Global-10 Short Form to establish baseline measurement again. Women of childbearing potential will undergo a urine pregnancy test prior to receiving the nerve block.

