If VAS < 5 on the pain scale, participants will not be eligible for second trigeminal nerve block during the visit. Study nurse will continue monitoring the participant's pain intensity (daily through day 15, and weekly thereafter) to see if the participant pain is above 5 on the pain scale and eligible for the second block. In general, the study intends that participants would receive both treatments unless they experience intolerable toxicity. If a participant is unable or ineligible to receive second trigeminal nerve block, then the participant's data collected during the first nerve block will be included in the analysis. In addition, a replacement participant will be enrolled so that the minimum number of 30 for each arm is reached. An intention-to-treat analysis will be done post-hoc to evaluate any differential progress to second block between the initial randomized groups.

Second trigeminal nerve block procedure: Participant will receive second trigeminal nerve block followed by monitoring for pain intensity at 30-minute time intervals for the first 8 hours after block, again allowing responses all the way until the next time point.

Second follow-up period (14 days)

Participants will be monitored once daily at the same timepoint for 14 days using text message generated using the Twilio application or recorded on a paper diary. Participants will also be monitored for any use of rescue medication (analgesics) once daily. The study nurse will monitor participants once weekly for overall quality of life via phone call. Participants will be instructed to contact the study nurse with any adverse events directly by phone.

[figure not shown]

Figure: 1. Study Schema

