The trigeminal block procedure is standard of care in the pain clinic. Expected effects of successful block include transient numbness, transient facial weakness including ipsilateral eyelid lag, and rare visual changes all of which resolve with the resolution of the effects of lidocaine over the typical course of 2 hours. Rare risks of the block procedure include infection, bleeding, nerve injury from the mechanical placement of the block needle. Rare risks of using lidocaine during the block procedure include intravascular or subdural injection resulting in transient unresponsiveness and/or seizure, mild sedation, bradycardia, and arrhythmias. These rare risks and side-effects must be differentiated from potential side-effects due to the addition of guanfacine. As all eligible patients are in

clinic for diagnostic nerve block as standard of care, they will receive clinical consent to treatment for the injection procedure itself and necessary x-ray radiation as part of routine care.

Common side-effects of daily oral use of guanfacine include dizziness, drowsiness, tiredness, low blood pressure, and slow heart rate. These side-effects are similar among other medications in the same class including clonidine, dexmedetomidine, tizanidine. Clonidine is also used as an intrathecal analgesic and as a perineural adjunctive injectate for regional blocks. We would expect that the side-effects of guanfacine as an adjunct to lidocaine block might additionally include increased dizziness, drowsiness, tiredness, low blood pressure, and slow heart rate. If the level of sedation experienced by at least 20% of patients in either group is greater than anticipated either by severity or duration, study enrollment will be stopped and the safety monitor engaged for an interim review of data comparing the study groups. If oversedation is occurring in only one group, an adjustment will be made to maintain monitoring for more than an hour (as is standard) until complete recovery.

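### The pain-return time is not treated as interval-censored and unanswered prompts have no rule, so on the natural first-reply reading an excess of missed prompts on guanfacine would lengthen that arm's times without any analgesic effect

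*Combined protocol and SAP*

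**What the plan says.** The primary endpoint in section 2.0 is "time to return to baseline pain (VAS) measurement after treatment". Under Study Visit 2 in section 5.0, participants record "24- hour VAS and current VAS, before the procedure to establish a baseline pain score"; the text does not say which of the two scores is the threshold. They are then "monitored for pain intensity at 30-minute time intervals for the first 8 hours after block", with replies collected "while in the recovery (first 60 minutes) and after discharge home". Replies are accepted "with responses allowed all the way until the next time point and actual time of the response being used in analysis". The second block uses the same window: "again allowing responses all the way until the next time point".

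Section 9.0 analyses the time with a linear mixed model and a two-degree-of-freedom test. The only censoring it mentions is right censoring, which it regards as very unlikely. No section says whether return means a first or a sustained score, whether it means at or above baseline, or how an unanswered prompt is handled.

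On side effects, Safety Stopping Criteria in section 7.0 says that those of guanfacine as an adjunct "might additionally include increased dizziness, drowsiness, tiredness, low blood pressure, and slow heart rate". It gives no rate.

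**The concern.** Pain returns at some moment between the last reply below baseline and the first reply at or above it. If the later reply time is the event time, the recorded time is always too long, by an amount that grows with the gap between replies. The error cancels in the treatment comparison only if gaps are alike under both treatments.

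A participant who sleeps through prompts has longer gaps. If that happens more often after guanfacine, the guanfacine times move later for a reason unrelated to pain. Blinding and the crossover do not remove this, because the gaps follow the drug received. The error favours guanfacine on the primary endpoint of a proof-of-mechanism trial whose design effect, 28 min, is shorter than one prompt interval.

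**Working it through.** **Inputs from the plan.** Control mean 140 min, difference 28 min, between- and within-subject SD 30 min each, 30 participants (sections 9.0 and 9.1); two-degree-of-freedom test at 5% (section 9.0); prompts every 30 min to 480 min, the first 60 min in recovery (section 5.0).

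**The plan's own power.** The SD of a within-participant difference is 30 × √2 = 42.4 min. Noncentrality = 30 × 28² / 1800 = 13.07. Power is 90.9% for the chi-square form of the test and 87.5% for the F(2, 28) form. The stated figure of approximately 90% is reproduced.

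**Where returns are recorded.** The total SD of a return time is √(30² + 30²) = 42.4 min. Since (60 − 140)/42.4 = −1.89, about 97% of returns fall after the first hour, when participants are at home.

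**Size of the lag.** For a gap L between replies, the mean lag of the right-end rule is E[L²] / (2E[L]). With prompts 30 min apart, each missed independently with probability m, this equals 15(1 + m)/(1 − m):

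- m = 5%: 15 × 1.05/0.95 = 16.6 min
- m = 10%: 15 × 1.10/0.90 = 18.3 min
- m = 15%: 15 × 1.15/0.85 = 20.3 min
- m = 25%: 15 × 1.25/0.75 = 25.0 min
- m = 40%: 15 × 1.40/0.60 = 35.0 min

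Against 5% in the control arm, the expected spurious differences are 1.8, 3.7, 8.4 and 18.4 min.

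**Simulation under the planned test.** Return times have the same distribution in both arms and no prompts are missed in the first 60 min. The event is the first reply at or above baseline, and the test is the two-degree-of-freedom test in F form. Miss rates and sleep spells are assumptions, because the documents give none.

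| Assumed pattern (control vs guanfacine) | Spurious difference | False positives |
|---|---|---|
| 5% vs 10% missed | about +2 min | 5% |
| 5% vs 15% missed | +3.6 min | 6–7% |
| 5% vs 25% missed | +8 min | 11% |
| 5% vs 40% missed | +18 min | 28–30% |
| 1-h sleep in 20% of guanfacine blocks | +3.6 min | 6% |
| 2-h sleep in 20% of guanfacine blocks, starting 1–3 h after the block | +11 min | 12–13% |

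Relative to the 28-min design effect, 8, 11 and 18 min are 29%, 39% and 64%. Equal miss rates (10% vs 10%) give no bias and about 5% false positives.

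**Late but answered prompts.** Delays of up to 29 min on guanfacine against up to 5 min on control, with nothing missed, give +2.8 min and 6%. The harm comes from prompts never answered.

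**Midpoint instead of reply time.** Placing the event midway between the last reply below and the first reply at or above baseline cuts every row of the table to about 3 min or less, with false positives of about 5–6%. With a true 28-min effect and equal miss rates, power is about 82–83% with midpoints and 80–81% with reply times. In a more extreme case, 10% vs 50% missed, the reply-time rule gives +25.8 min and 47%; the midpoint leaves +4.3 min and 6%.

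**The case against.** The strongest reply is that the bias depends on a rule the plan never states. A reader might infer that the plan defines return as the first reply at or above baseline. It does not. That is the natural reading of sections 2.0, 5.0 and 9.0 together, but only a reading. This limits the claim to a conditional one; it also shows that the event needs defining.

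A reader might also blame the sentence on actual reply times. That would be wrong. Late replies do little harm, nominal prompt times would carry the same missed-prompt error, and the recorded reply times are what make the midpoint possible.

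On sedation, section 1.0 says "Of the alpha-2 agonists, guanfacine has the lowest rate of sedation", section 6.0 counts sedation among risks seen as low, and section 7.0 lists mild sedation as a rare risk of lidocaine too. The first statement compares guanfacine with its own class, not with lidocaine alone, so it does not show equal drowsiness between arms. Still, section 7.0 says only that added drowsiness might occur, and nothing in the documents links drowsiness to missed prompts. The 20% in section 7.0 must not be read as an expected rate: it triggers a pause in enrolment and a safety review. If oversedation occurs in one group only, that section extends monitoring, which would reduce unattended missed prompts.

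Finally, small imbalances and 1-h spells hardly matter. That stands.

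**Conclusion.** The concern holds as a conditional risk to the primary endpoint. The plan has no rule for unanswered prompts and does not treat the return time as interval-censored. On the natural first-reply reading, an excess of missed prompts on guanfacine lengthens that arm's times without analgesia.

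The size runs from about 2 min with no inflation of the error rate (5% vs 10% missed), through 8–11 min with 11–13% false positives (5% vs 25%, or 2-h sleeps in 20% of guanfacine blocks), to 18 min with 28–30% (5% vs 40%). All miss rates and sleep patterns are assumptions, including the 20% share. A reader might infer that sedation alone would be likely to produce the whole 28 min. The documents do not support that: they give no rate of drowsiness or missed prompts, and matching the design effect takes roughly half of guanfacine prompts missed, or multi-hour spells in a sizeable share of blocks. The change is still worth making, because it is cheap and removes most of the bias wherever in this range the truth lies.

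**What to change.** In sections 5.0 and 9.0:

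1. State which baseline score, 24-hour or current VAS, is the threshold, and that return is the first reply at or above it.
2. Treat the return time as interval-censored between the last reply below the threshold and the first reply at or above it, using actual reply times; an unanswered prompt simply widens the interval.
3. Use the interval midpoint in the planned linear mixed model, with an interval-censored model as sensitivity analysis.
4. Tabulate missed prompts and gap length by treatment beside the primary result.

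The cost is a few sentences and a little extra analysis. The plan already collects the reply times, so no new data or patients are needed. The drawback is a small residual bias when gaps are long, which the sensitivity analysis and the table of gaps would help a reader judge.

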5.0 STUDY PROCEDURE

The study is a single center, randomized, double-blind, 2 x 2 crossover pilot study with two arms; study drug (guanfacine and lidocaine combination) and active control (lidocaine alone). Adult participants between 18 and 80 years of age who have been diagnosed with painful trigeminal neuropathy will be consented for the study. The study includes three visits; an initial visit for evaluation, consent, and baseline surveys followed by two procedural visits. After each procedural visit data will be collected for 14 days. Participants will be randomized in permuted pairs (to ensure balance after every second enrollment) to receive either study drug (guanfacine and lidocaine combination) or active control (lidocaine alone) for the first nerve block procedure. Following the first procedural visit and 14-day follow up period, the study team will assess inclusion and exclusion criteria and (if eligible) schedule the second procedural visit.

Assessment	Study Visit 1: Consent and screening (Day -15 to 0)	Study Visit 2: Procedure 1 (Day 1)	Follow-up period 1 (Day 2-14)	Study Visit 3: Procedure 2 (≥15 days after procedure 1)	Follow-up period 2 (14 days after procedure 2)
		Administrative P	rocedures		
Eligibility Review	X	X		X	
Informed Consent	X				
Demographics	X				
Pain History	X				
Baseline Pain	X	X	X	X	X
Medical History	X				
Concomitant Medications	X	X		X	
Surgical/ Past Treatments History	X				
Verbal Pregnancy Screen	X				
PROMIS Global 10- SF	X	X	X \$	X	X \$
Pain Interference	X	X		X	
Pain Intensity (VAS Score)	X	X #	X %	X #	X
Frequency of Attacks	X	X	X \$	X	X \$
Rescue Medications		X %	X %	X %	X
Randomization	X				
	Cl	inical Procedures/	Assessments		•
Physical Exam (general)	X	X		X	
Physical Exam (pain)	X				
Vitals (HR, RR, Temp, BP)	X	X		X	
Height/ Weight	X				
12-Lead ECG ^	X				
Continuous ECG monitoring		X		X	
Nerve Block Administration		X		X *	
Imaging MRI/ CT report +	X				
Adverse Events		X	X	X	X
		Laboratory Pro	cedures		
Urine Pregnancy Test		X		X	
Urine Drug Screen	X				

^{#:} Collected every 30 minutes for 8 hours by text message (REDCap) or patient diary

^{%:} Collected daily for up to 28 days by text message (REDCap) or patient diary

Collected weekly for up to 4 weeks by study nurse phone call

If pain score >5

^{+:} Review recent imagining, if not available then order as standard of care
^: Order 12-lead ECG as standard of care if one not available within 2 months of screening visit

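### Pain is not read between 8 h after the block and the first daily text, so a return to baseline in that gap is known only to within about 8 to 24 h against a 28-minute target

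*Combined protocol and SAP*

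**What the plan says.** Section 2.0 defines the primary endpoint as "time to return to baseline pain (VAS) measurement after treatment with guanfacine as adjuvant to 1% lidocaine", compared with lidocaine alone. Section 5.0 sets the sampling: "Participants will be monitored for pain intensity at 30-minute time intervals for the first 8 hours after block". The schedule footnote agrees: "Collected every 30 minutes for 8 hours by text message (REDCap) or patient diary". Replies are accepted "with responses allowed all the way until the next time point and actual time of the response being used in analysis".

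After that the frequency drops. For the first period, "Participants will be monitored once daily at approximately the same timepoint for 14 days using text message"; for the second, "Participants will be monitored once daily at the same timepoint for 14 days using text message". In the schedule table the pain VAS on both procedure days carries only the 30-minute code, so no pain reading is scheduled between 8 h and the first daily one.

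Section 9.0 analyses the time with a linear mixed model. It mentions right censoring only as very unlikely, does not mention interval censoring, and leaves other models to be considered as needed. No section says what time is assigned to a return that falls between two readings.

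On how long relief may last, the documents point two ways. Section 9.1 plans a control mean of 140 minutes and a 28-minute gain, and its closing paragraph speaks of 28 to 70 extra minutes. Section 7.0 describes lidocaine effects as lasting typically about 2 hours. Section 1.0, by contrast, says that drugs of this class extend regional blocks by several hours. It gives animal guanfacine effects of 8 h and, in rats, "intrathecal guanfacine has shown antinociceptive effect for greater than 18 h", and says the drug "has an elimination half-life of ~17 h". Sections 5.0 and 9.1 also provide for participants whose VAS is still below 5 at the second procedural visit.

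**The concern.** Using the actual reply time fixes when an answer arrived, not when pain came back between two answers. Inside the first 8 h this hardly matters. The 30-minute grid delays a recorded return by about 15 minutes on average in both arms, and the delay cancels in the difference. Beyond 8 h the spacing widens to many times the target effect, and the cancellation fails if long responses are commoner after guanfacine.

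Two things are at stake. If the return is dated to the later reading, long responses are lengthened, and the treatment effect with them when they fall mainly in the guanfacine arm. A few very large values also inflate the residual variance of a linear model planned with SDs of 30 minutes, which can conceal an effect that is there.

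**Working it through.** **1. The plan's own figure.** Inputs from section 9.1: 30 participants, difference 28 min, between- and within-participant SD 30 min each; two-sided 5% and the two-degree-of-freedom test from section 9.0.
- SD of the within-person difference = 30 × √2 = 42.4; SE = 42.4/√30 = 7.75; noncentrality = (28/7.75)² = 13.07.
- Power of the 2-df chi-square test = 90.9%. The stated figure of about 90% reproduces.

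**2. Does anyone reach 8 h on the planning values?** The total SD of one time is √(30² + 30²) = 42.4 min, and 8 h is 480 min. For a guanfacine mean of 168: (480 − 168)/42.4 = 7.4 SD. For 210: (480 − 210)/42.4 = 6.4 SD. On these values, practically nobody does. From the control mean, relief would have to be extended by 480 − 140 = 340 min (5 h 40 min) to reach the gap. That is within reach of an effect of several hours or of the animal durations, but far outside the planning values.

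**3. Width of the gap.** The clock time of the daily reading is not given; 16 to 32 h after the block is assumed. The last column takes a true return at 9 h, recorded at the daily reading, in one of 30 participants: (reading − 9 h) × 60/30.

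| First daily reading | Gap after 8 h | Gap ÷ 28 min | Shift of arm mean |
|---|---|---|---|
| 16 h | 480 min | 17 | 14 min |
| 18 h | 600 min | 21 | 18 min |
| 24 h | 960 min | 34 | 30 min |
| 32 h | 1,440 min | 51 | 46 min |

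With a 24 h reading, a true return at 12 h shifts the mean by 24 min and one at 16 h by 16 min.

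**4. Bias if long responses occur only after guanfacine.** Assume a share p of guanfacine blocks return uniformly between 8 and 18 h (mean 780 min). All other blocks in both arms average 154 min (midway between 140 and 168), and the reading is at 24 h (1,440 min). The true difference is p × (780 − 154); dated to the later reading it is p × (1,440 − 154); dated to the gap's midpoint (960 min) it is p × (960 − 154).

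| p | True | Later reading | Midpoint |
|---|---|---|---|
| 1% | 6 | 13 | 8 |
| 2% | 13 | 26 | 16 |
| 5% | 31 | 64 | 40 |

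These are minutes. A simulation on the full grid gives the same to within a minute or two.

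**5. Noise if both arms have 5% long responses.** Other times have variance 42.4² = 1,800; the long times have variance 600²/12 = 30,000.
- True times: 0.95 × 1,800 + 0.05 × 30,000 + 0.0475 × 626² = 21,824 per block. SD of the paired difference = √(2 × 21,824) = 209 min.
- Later reading: 1,710 + 0.0475 × 1,286² = 80,265; SD 401 min.
- Midpoint: 1,710 + 0.0475 × 806² = 32,568; SD 255 min.
- Hourly prompts answered to 16 h, each return dated to the later reading: about 250 min (simulation).

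**6. One long response in the planned test.** Take 29 differences as planned and one guanfacine response truly lasting 12 h. The mean difference is (29 × 28 + 720 − 140)/30 = 46 min if timed correctly, and (29 × 28 + 1,440 − 140)/30 = 70 min if recorded at 24 h. Simulated power of the 2-df test (20,000 runs, 15 per sequence) is 59% and 0.3%: the estimate rises and the test fails.

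**The case against.** The strongest reply is that the trial does not expect such responses. Planned means are 140 to 210 min, the dense window is more than three times the control mean, and section 9.1 defers considerably longer relief to a later formulation. This stands as far as it goes. It rules out the inference that the grid is blind exactly where the planned effect lies.

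The background figures are also indirect. The 17 h is an elimination half-life given beside oral bioavailability, not a duration of block. The 8 h and >18 h effects come from animals, the latter intrathecal in rats, and an 8 h effect sits only at the edge of the dense window. Participants with VAS below 5 at the second visit may have passed through the gap without returning in it. These passages make a return in the gap foreseeable; they do not predict one.

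A reader might also infer that every such return will be recorded late and the effect inflated. The documents do not say so: no timing rule exists, and late recording is an assumption made here. With long responses equally common in both arms the result is noise, and step 6 shows that a missed effect is as possible as a false gain.

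Finally, a reader might infer that no analysis could repair the gap. That holds only for the individual return time. On the existing grid, the midpoint brings the SD from 401 to 255, about what hourly prompts achieve, and the reply times already collected supply both ends of the interval.

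What remains is a gap at a foreseeable place, no rule for handling it, and a cheap way to narrow it before data are collected.

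**Conclusion.** The concern holds in conditional form. After both blocks, a return to baseline between 8 h and the first daily reading is known only to within about 8 to 24 h, which is 17 to 51 times the target difference. The planning values imply that almost nobody is exposed, while the background and the second-visit rule foresee longer relief; the documents disagree on this.

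If such a return is dated to the later reading, one participant in 30 returning at 9 h moves the arm mean by 14 to 46 min. It exceeds 28 min at a 24 h or 32 h reading but not at 16 h or 18 h. At assumed rates of 1%, 2% and 5%, confined to guanfacine and with a 24 h reading, the effect is roughly doubled (6 to 13, 13 to 26, 31 to 64 min). The reading time, the long-response rates, the 8 to 18 h spread and the late-recording rule are all assumptions. The change is worth making because it costs almost nothing if the planning values prove right.

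**What to change.** In section 5.0, for both periods, continue the existing REDCap/Twilio or diary VAS prompt after 8 h only for participants not yet back at baseline: for example hourly while awake, plus one prompt on waking on Day 2. Stop once a return is recorded. State the intended clock time of the daily reading.

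In section 9.0, specify that a return between two readings is analysed as an interval, from the last below-baseline time to the first at-baseline time. At minimum, use the midpoint, not the time of the later reading. Section 9.0 already allows packages beyond lme4 if the interval model needs one.

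The cost is a change to an automated text schedule and diary page, a few extra prompts for long responders, and a short addition to the analysis text. Overnight returns stay interval-timed: if prompts lapse from about 12 to 13 h until waking at 21 h (assumed), the SD in step 5 is about 269 to 283 rather than about 250 min. Neither change removes the leverage of a genuinely long response. Even with true times, the SD of the paired difference in that example is 209 min against the planned 42.
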